4 STUDY DESIGN

4.1 Overall design

This is a prospective, exploratory, cohort study to evaluate the baseline and post-vaccination immune responses in individuals with select immune deficiencies compared to healthy volunteers who receive a COVID-19 vaccine, as well as any AEs experienced after vaccinations. Due to the ongoing pandemic and limited availability of vaccines at the time of preparation of this protocol, participants will receive vaccine externally (i.e., via private physicians or community resources, and not as study interventions). Study visits may be conducted in person or remotely. If participants cannot attend in-person visits at the NIH CC, they can choose to have blood drawn at a primary care provider, academic hospital laboratory, or Quest Diagnostics, as

necessary, and will be sent sampling kits containing all tubes and instructions for the drawing facility. All participants will also be provided with microsamplers kits and mailing supplies to collect and send in fingerstick samples if they are unable to obtain venous blood samples at an off-site facility. Participants will be asked to provide samples at baseline (collected within 7 days prior to receiving the vaccine), 14-28 days (depending on vaccine manufacturer and platform) after dose 1 and 21-28 days after dose 2 (if applicable). Samples will be requested from participants as scheduled after each vaccination (+/- 7 days) however samples received outside of the requested windows are acceptable and will be analyzed at the discretion of the PI.

Participants may enroll after vaccination was already performed. If these individuals do not have current plans for an additional booster dose, previous timepoint samples will not be obtained and they will proceed with the next relevant sampling timepoint. In this situation, if stored blood samples from studies in which subjects are concurrently enrolled are available, they will be used, otherwise they will be waived. If these individuals plan to receive an additional booster vaccination(s), they will be enrolled prior to the booster dose and follow the normal schedule, including a baseline draw prior to the booster.

Participants who are able to come to the NIH will have the additional option to provide blood samples at days 1 and 3 after each vaccination in order to capture immediate vaccine-induced perturbations of immune responses. Samples will be used to study short-term immunological effects of immunization and boosting. If additional booster doses are received, participants will be asked to submit optional blood samples 21-28 days after the booster vaccination(s), through the 5th dose of a COVID-19 vaccine. Samples received outside of that window samples received outside of the requested windows are acceptable and will be analyzed at the discretion of the PI. Additional optional blood samples may be provided at approximately 6, 12, and 24 months after the final vaccination to assess long-term immunological persistence of vaccine-derived antibodies and T-cell responses. Research evaluations on these samples will include baseline and post-vaccine autoantibody levels as well as SARS-CoV-2 antibody titers to the S, N, and RBD proteins. Serology has been validated across fresh serum and dried blood samples collected using microsamplers (see Figure below)⁸. Venous blood draw may be waived if a participant is unable to obtain it at any given timepoint.

[figure not shown]

Figure 1. Quantification of antibody concentration utilizing 4PL sigmoidal model of recombinant antibody spiked into seronegative blood. **A)** Anti-RBD recombinant human antibody (IgG and IgM) was added to whole blood from two seronegative donors, then absorbed to microsamplers and remaining blood was spun down to isolate serum and analyzed on full spike ectodomain trimer (spike) or receptor-binding domain (RBD) ELISA. Data are mean \pm SEM, n = 3, red = microsampler eluate, gray = matched serum. **B)** Direct comparison of absorbance of range of recombinant antibody concentration in serum (y axis) versus microsampler (x axis) blood samples. **C)** Sigmoidal four-parameter logistic (4PL) curve fitting to recombinant antibody dilution series, 95% confidence intervals shown shaded around fit curve, n = 12 replicates per data point, red = Spike IgG, orange = RBD IgG, blue = Spike IgM, purple = RBD IgM. **D)** Quantification of IgG levels in a sample high-incidence population. **E)** Upper limit of quantification at 1:400 dilution of serum into ELISA (1:10 dilution of microsampler eluate), n = 68. From ref⁸

Additional research evaluations include analysis of the nature, diversity, and frequency of SARS-CoV-2 specific T- and B-cell receptor clonotypes. These evaluations will be used to assess pre-vaccination SARS-CoV-2 exposure and expected response to vaccination. Additional research evaluations may include virus neutralization assays to assess antibody functional response, flow cytometry, and transcriptome and genetic analyses. Comparisons of the immune response will be made among immunodeficiency/dysregulation subtypes and against healthy controls. This will allow characterization of the differences in post-vaccination immune responses and AE presentation.

Subjects will be asked at baseline about prior COVID-19 diagnosis, symptoms, and severity using standardized questionnaires. This will allow us to characterize the different manifestations of COVID-19, potentially including a lack of hyper-inflammatory symptoms associated with severe disease due to dysregulation of the immune response that will be present in many of the study participants. To conduct active screening for post-vaccination COVID-19 infections, participants will be sent optional saliva collection kits to return to the NIH bi-weekly for 6 months, for PCR and genetic sequencing of the virus. Participants whose samples are PCR positive will be asked to submit an additional COVID-19 symptom questionnaire and will be referred for care as needed. Each time a participant receives an additional booster dose while they are still on study (through the 5th COVID-19 vaccine a person receives), they may participate in optional bi-weekly saliva collections for an additional 6-month period. Since this is optional, saliva samples received outside of the requested windows are acceptable and will be analyzed at the discretion of the PI. At follow-up timepoints, participants will be asked about all possible vaccine-related AEs, which will be particularly important given recent information about possible vaccine-induced anaphylaxis.

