1.2 Schedule of Activities

Evaluation	Study Day (window)							
	Screening and Baseline*	Vaccine dose 1 Follow-up			Vaccine dose 2 Follow-up [‡]			Optional Follow-up [†]
	-7 to 0	1 day after vaccination [§]	3 days after vaccination [§]	14-21 OR 21-28 days after vaccination ^{**}	1 day after vaccination [§]	3 days after vaccination [§]	21-28 days after vaccination ^{**}	6, 12, and 24 months (±2 weeks) after last vaccination
Informed consent	X							
Clinical Procedures and Evaluations								
COVID-19 history and symptom questionnaire	X							
Baseline medical history and screening questionnaire	X							
Changes in medical history questionnaire				X			X	X
Electronic AE questionnaire [^]				X			X	
Behavioral questionnaire							X	
Clinical Laboratory Evaluations ^{^^}								
Blood Volume (mL)								
CBC with differential	3 mL	4 mL	4 mL	3 mL	4 mL	4 mL	3 mL	
TBNK lymphocyte phenotyping/flow/cytok		[X]	[X]		[X]	[X]		

Research Laboratory Evaluations ^{^^}	Blood Volume (mL)							
	0.8 mL	0.8 mL	0.8 mL	0.8 mL	0.8 mL	0.8 mL	0.8 mL	0.8 mL
Mitra microsampler [¶] 
 SARS-CoV-2 antibody (S, RBD, N – IgG, IgM, IgA) Autoantibodies 	0.8 mL			0.8 mL			0.8 mL	0.8 mL
Serum (red cap) ^{††} 
 Neutralizing SARS-CoV-2 antibodies 	5 mL	5 mL	5 mL	5 mL	5 mL	5 mL	5 mL	5 mL
Plasma isolation (EDTA purple cap) [¶] 
 DNA isolation (for high throughput sequencing of TCR/BCR repertoire and for genetic studies) 	10 mL	10 mL	10 mL	10 mL	10 mL	10 mL	10 mL	10 mL
PAXgene tube ^{††} 
 Whole blood RNA 	2.5 mL	2.5 mL	2.5 mL	2.5 mL	2.5 mL	2.5 mL	2.5 mL	2.5 mL
PBMC isolation (sodium heparin green top OR EDTA purple cap) ^{††} 
 Lymphocyte/plasmablast Functional T cells 	10 mL	10 mL	10 mL	10 mL	10 mL	10 mL	10 mL	10 mL
Saliva ^{‡‡} 
 SARS-CoV-2 PCR and sequencing 	Bi-weekly through 6 months							
Daily Blood Volume	31.3 mL	31.5 mL	31.5 mL	31.3 mL	31.5 mL	31.5 mL	31.3 mL	31.3 mL
Cumulative Blood Volume	31.3 mL	62.8 mL	94.3 mL	125.6 mL	157.1 mL	188.6 mL	219.9 mL	251.2 mL (6 mos.) 282.5 mL (12 mos.) 313.8 mL (24 mos.)

[X] = will be performed with portion of sample collected for CBC with differential and does not require additional volume.

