Abbreviations: AE, adverse event; BCR, B cell receptor; CBC, complete blood count; COVID-19, coronavirus disease 2019; DNA, deoxyribonucleic acid; EDTA, ethylenediaminetetraacetic acid; Ig, immunoglobulin; PBMC, peripheral blood mononuclear cell; N, nucleocapsid; RBD, receptor binding domain; RNA, ribonucleic acid; S, spike; SARS-CoV-2, severe acute respiratory syndrome coronavirus 2; TBNK, T, B, and natural killer (cells); TCR, T cell receptor; NP, nasopharyngeal; OP, oropharyngeal; PCR, polymerase chain reaction.

*Baseline sampling and questionnaire can happen on the day of vaccination as long as it is prior to receiving the dose. Participants may enroll after vaccination was already performed. If these individuals do not have current plans for an additional booster dose, previous timepoint samples will not be obtained and they will proceed with the next relevant sampling timepoint. In this situation, if stored blood samples from studies in which subjects are concurrently enrolled are available, they will be used. If stored samples are not available, these samples will be considered waived. If these individuals plan to receive an additional booster vaccination(s), they will be enrolled prior to the booster dose and follow the normal schedule, including a baseline draw prior to the booster.

**The exact timing of these visits will depend upon vaccine manufacturer and platform (as detailed in the Manual of Procedures) but will fall within the ranges indicated. For subjects who decline participation in the optional long-term follow-up visits, study completion will end after the dose 1 or 2 follow-up visit(s), depending on whether the subject received a 1-dose or 2-dose vaccine. Each time a participant receives an additional booster dose while they are still on study, a 21-28-day visit will be performed, and optional long-term follow-up visits will be offered. Samples will be requested from participants as scheduled after each vaccination and booster (+/- 7 days) however samples received outside of the requested windows are acceptable and will be analyzed at the discretion of the PI.

‡ Not all vaccines require a second dose and therefore these follow-up timepoints will be not applicable for participants receiving those vaccines.

^AE questionnaire will be administered after any additional booster dose.

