Electronic questionnaires: Five separate Research Electronic Data Capture system (REDCap) questionnaires will be completed electronically in REDCap by subjects and/or their parents/guardians throughout the study. A link to the questionnaires will be sent to the personal email address on file. The baseline questionnaire will capture medical history, and any COVID-19 symptoms, severity, and treatment the participant may have experienced. The follow-up questionnaires will assess changes in health history or medications and AEs following study vaccination. An optional survey will ask participants about their beliefs and behaviors around COVID-19 vaccinations, and whether they have changed since before the primary vaccine series and/or booster doses. The questionnaires and their timing are listed below:

1. Baseline medical history and screening questionnaire (Baseline)
2. COVID-19 baseline/post-vaccine infection symptom questionnaire (Baseline and following COVID-19 infection)
3. Changes in medical history questionnaire (Following sample collection)
4. Post-vaccine adverse events questionnaire (Following vaccination)

5. COVID-19 Attitudes and Behaviors Survey (Following primary series and/or booster)

AE assessment: Only AEs related to study procedures (blood draw, fingerstick, and saliva collection) will be followed. COVID-19 vaccines are not administered as study procedures under this protocol; therefore, while we are interested in collecting AEs related to vaccination in our study population, these are not considered study-related events and will not be followed as such. Subjects will be assessed for AEs at each study visit. Information on AEs related to the study procedures that develop within 2 days after the procedure will be collected by participant report and followed through resolution or until the site investigator judges that the event has stabilized and no additional follow-up is required.

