8.4.2 Analysis of the Secondary Endpoints

We will calculate descriptive summaries, stratified by immune deficiency/dysregulation group, for incidence of vaccine-associated AEs listed in the Post-Vaccine Adverse Events questionnaire. Incidence of AEs among immune deficient/dysregulated patients will be compared with incidence among healthy volunteers using regression analyses, possibly adjusting for covariates, such as age and sex, as deemed appropriate.

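### Vaccine AEs are scheduled to be asked about only 2 to 4 weeks after each primary dose, and the plan fixes no onset window for the AE incidence that is its secondary endpoint

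*Combined protocol and SAP*

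**What the plan says.** The only secondary endpoint (synopsis and section 3) is the incidence of vaccine-associated AEs in patients with immune deficiency or dysregulation compared with healthy volunteers. Four places bear on how it is measured.

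- **Section 4.1:** "At follow-up timepoints, participants will be asked about all possible vaccine-related AEs".
- **Section 1.2, schedule:** the row "Electronic AE questionnaire" is marked in two columns only. One is the dose-1 visit, "14-21 OR 21-28 days after vaccination"; the other is the dose-2 visit at 21-28 days. Nothing is marked at days 1 and 3 or at 6, 12 and 24 months. The footnotes add: "The exact timing of these visits will depend upon vaccine manufacturer and platform", with details in a Manual of Procedures, and "AE questionnaire will be administered after any additional booster dose". No day is given for the booster form; the booster visit is at 21-28 days.
- **Section 7.2:** "A link to the questionnaires will be sent to the personal email address on file". The list of questionnaires times the AE form only as following vaccination, whereas the form on changes in medical history is tied to sample collection.
- **Section 8.4.2:** descriptive summaries by immune group of "incidence of vaccine-associated AEs listed in the Post-Vaccine Adverse Events questionnaire", then a regression against healthy volunteers that may adjust for covariates, with age and sex as examples.

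**The concern.** Two problems follow if the schedule governs.

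The first is recall. Reactions that pass within days are asked about 14 to 28 days later. No diary or earlier enquiry about vaccine AEs is described, and the optional day 1 and day 3 visits at the NIH carry no AE form.

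The second is the missing definition of the period at risk. Without a stated onset window, a participant who answers on day 28 has had twice as long to accumulate reportable events as one who answers on day 14. Incidence by immune group then mixes reactogenicity with length of observation. If product or promptness of reply differs between patients and healthy volunteers, part of any difference in 8.4.2 could come from timing alone, or a true difference could be hidden.

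**Working it through.** The documents state no AE rate, sample size or power for this endpoint, so there is no planned figure to reproduce. The check has two parts.

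**1. Reporting periods on schedule (from 1.2)**

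| Dose | Form scheduled | Longest / shortest period |
|---|---|---|
| Dose 1 | day 14-21 or 21-28, by product | 28/14 = 2.0 |
| Dose 2 | day 21-28, all products | 28/21 = 1.33 |
| Booster | no day stated; visit at day 21-28 | 28/21 = 1.33 if sent at the visit |

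Product-dependent timing is therefore a dose-1 matter. Recall of 2 to 4 weeks applies to dose 1, and of 3 to 4 weeks to dose 2 and, if the form follows the visit, to boosters.

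**2. Size of a timing artefact at dose 1**

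Assumptions, none of them from the documents: constant background rate r per day, the same in both groups; no vaccine effect; a question that runs from vaccination to the day of reply. Incidence by day d is 1 - (1 - r)^d.

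*Extreme case: one whole group replies on day 14 and the other on day 28.* At r = 1%:
- day 14: 1 - 0.99^14 = 13.1%
- day 28: 1 - 0.99^28 = 24.5%
- ratio 24.5/13.1 = 1.87

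*Moderate case: replies at mid-window (day 17.5 or 24.5), with 40% of one group and 60% of the other on the later window.* At r = 1%:
- day 17.5: 1 - 0.99^17.5 = 16.13%; day 24.5: 1 - 0.99^24.5 = 21.83%
- group with 40% late: 0.6 × 16.13 + 0.4 × 21.83 = 18.41%
- group with 60% late: 0.4 × 16.13 + 0.6 × 21.83 = 19.55%
- difference 1.14 points, ratio 19.55/18.41 = 1.06

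| r per day | Day 14 v day 28 | Ratio | Difference with 20-point imbalance |
|---|---|---|---|
| 0.5% | 6.8% v 13.1% | 1.93 | 0.63 points |
| 1% | 13.1% v 24.5% | 1.87 | 1.14 points |
| 2% | 24.6% v 43.2% | 1.75 | 1.85 points |

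Setting the background risk at 5% to 30% per 28 days instead gives the same picture. The ratio for day 28 v day 14 is 1.97 to 1.84, and the 20-point imbalance yields 0.25 to 1.4 points. With 100 healthy volunteers and 400 patients (synopsis; 8.2 gives 120 healthy volunteers), the chance of a significant result in the direction of the artefact at two-sided 0.05 is 14% to 82% when timing is fully aligned with group. With the 20-point imbalance it is about 3% to 5%, against a nominal 2.5% in that direction.

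With one fixed onset window for everyone, the period ratio is 1 and this artefact is zero by construction. Loss through recall cannot be sized, because the documents give nothing on it.

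**The case against.** Several stronger readings are tempting and do not hold.

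- **A 7 to 35 day range for replies.** The ±7 days in 1.2 and 4.1, and the rule that "samples received outside of the requested windows are acceptable and will be analyzed at the discretion of the PI", are written for samples. An e-mailed form need not follow sample lateness. What can be said is that no window or deadline is stated for the form.
- **The comparison is biased by a factor of about 1.9.** That needs timing to coincide entirely with group. No section gives product mix or reply delay by group, so imbalance is a possibility and not a finding. Unequal periods that are alike in both groups do not by themselves create a group difference. For reactions that end within days, the later weeks also add little.
- **8.4.2 compares raw incidence.** It specifies a regression with an open list of covariates, so product and time since dose could be added.
- **The form is sent only at the sampling visits.** The schedule says so, but the list in 7.2 ties it to vaccination. The two are unreconciled.

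The questionnaire and the Manual of Procedures are not among the documents and may set a reporting period. The study is exploratory, and the vaccines are given outside it.

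These points limit the size. They do not supply an onset window in the plan or, if the schedule governs, an earlier enquiry. The statement in 7.2 that AEs are assessed at each visit does not fill the gap: it stands in a paragraph that follows up only AEs of study procedures, gives those a 2-day onset window, and sets none for vaccine AEs. A reporting period on the form would equalise the periods but not shorten the recall.

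**Conclusion.** The point holds in a limited form and should be acted on. As scheduled, vaccine reactions are recalled 2 to 4 weeks after the dose, and the plan's text defines no onset window for its only secondary endpoint. On-schedule dose-1 periods can differ up to 2-fold. Descriptive incidences by group are affected in any case.

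The comparison of patients with healthy volunteers is biased by the unequal periods only if product or reply delay differs by group. The plan does not prevent this: controls are enrolled to be representative on age and sex (8.2), and 8.4.2 names neither product nor time since dose. On the assumed background rates of 0.5% to 2% per day, a moderate product imbalance costs about 0.6 to 1.9 points. The near-doubling is an upper bound for on-schedule replies. All these figures assume an open question about events since vaccination.

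**What to change.** 1. Reconcile the schedule in 1.2 with the questionnaire list in 7.2, and state the day on which the AE form is sent after each dose, boosters included.
2. Send the existing REDCap link at day 7 after every dose, asking about days 0-7, and again at the sampling visit for later events. Record the onset date of each event and the completion date of each form.
3. In 8.4.2, define the endpoint as AEs with onset in days 0-7, the same for every product and group. Report later events separately in a second fixed window, for example days 8-14.
4. Include vaccine product and time from dose to reply in the AE regression.
5. Keep late day-7 forms in the main analysis. Exclude them (for example, those completed after day 10) only in a sensitivity analysis, because exclusion selects on promptness, which may itself differ by group.

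The cost is one extra short e-mailed form per dose, a schedule line and a few sentences in 8.4.2. Some day-7 forms will be missing, and participant burden rises slightly. If the extra form is declined, steps 1, 3 and 4 with onset and completion dates still equalise the periods, but the long recall remains.

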5 STUDY POPULATION

5.1 Inclusion Criteria

In order to be eligible to participate in this study, an individual must meet the following criteria:

1. Aged 3 years and older.
2. Must be eligible to receive (based on official FDA authorization or approval) and scheduled to receive or have already received a COVID-19 vaccine outside of this study.
3. Must meet the definition of affected participant or control participant:
 - a. Affected participants must have evidence of a primary or secondary immune deficiency or dysregulation under another NIAID protocol or as documented by an outside physician.
 - b. Control participants are healthy volunteers that do not have evidence of a primary or secondary immune deficiency or dysregulation and may include unaffected relatives of affected participants.
4. Ability to provide informed consent.
5. Willing to have blood samples stored for future research.
6. Able to proficiently speak, read, and write English.

5.2 Exclusion Criteria

Individuals meeting any of the following criteria will be excluded from study participation:

1. Receipt of any other vaccine within 14 days prior to screening.
2. Planned non-COVID-19 vaccination within 28 days after COVID-19 vaccination(s).
3. Any condition that, in the opinion of the investigator, contraindicates participation in this study (e.g. specific autoinflammatory diseases, interferonopathies).
4. Self-reported history of HIV.

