5.3 Inclusion of Vulnerable Participants

Children: As the immune deficiencies and dysregulations being studied under this protocol affect all age ranges, information gathered from all eligible children (both affected and control participants) will be important for providing a full understanding of any potential differential effects across age ranges. Children will only be enrolled if there is FDA authorization or approval for use of a COVID-19 vaccine in that age group.

Adult subjects who lack capacity to consent to research participation: Individuals who are unable to provide initial informed consent are excluded from the study. If participants lose the ability to provide ongoing consent subsequent to giving initial consent, they will be withdrawn from the study.

NIH staff or family members of study team members: NIH staff and family members of study team members may be enrolled in this study if they meet the study entry criteria. Neither participation nor refusal to participate in the research will have an effect, either beneficial or adverse, on an individual's employment or position at NIH.

Every effort will be made to protect subject information, but such information may be available in medical records and may be available to authorized users outside of the study team in both an identifiable and unidentifiable manner.

The NIH investigator will provide and request that the NIH staff member review the Frequently Asked Questions (FAQs) for Staff Who are Considering Participation in NIH Research and the Leave Policy for NIH Employees Participating in NIH Medical Research Studies (NIH Policy Manual 2300-630-3). Please see section 9.1.2 for consent of staff members.

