5.6 Screen Failures

Screen failures are defined as participants who consent to participate in the clinical study but are not subsequently entered in the study. Individuals who do not meet the criteria for participation in this study (screen failure) may be rescreened if they turn 12 before the study enrollment closes and have not yet received a COVID-19 vaccination, if the participant's time since non-COVID-

19 vaccination has passed 14 days and they remain unvaccinated for COVID-19, or their medical status changes such that the PI feels exclusion is no longer necessary.

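### The other-vaccine exclusion is timed to screening although screening need not fall near the COVID-19 dose, and the rescreening rule in 5.6 does not match entry under 5.1 and 5.3

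*Combined protocol and SAP*

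**What the plan says.** Section 5.2 has two consecutive rules on other vaccines, with different anchors. Exclusion 1 is "Receipt of any other vaccine within 14 days prior to screening". Exclusion 2 is "Planned non-COVID-19 vaccination within 28 days after COVID-19 vaccination(s)", which runs forward from the COVID-19 dose and reaches only vaccines that are planned. Section 5.6 restates the first rule as time since a non-COVID-19 vaccine.

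Screening is not fixed just before a dose. For prospective entrants, 4.1 says "Participants will be asked to provide samples at baseline (collected within 7 days prior to receiving the vaccine)", and the schedule in 1.2 gives the screening and baseline window as day -7 to 0. The same section says "Participants may enroll after vaccination was already performed", and inclusion 2 in 5.1 accepts people "scheduled to receive or have already received a COVID-19 vaccine outside of this study". Doses are followed through the fifth.

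On age, 5.1 requires "Aged 3 years and older", and 5.3 says "Children will only be enrolled if there is FDA authorization or approval for use of a COVID-19 vaccine in that age group". Section 5.6 gives three alternative rescreening routes. Under the first, a person "may be rescreened if they turn 12 before the study enrollment closes and have not yet received a COVID-19 vaccination". The second opens once 14 days have passed since the other vaccine, provided the person is still unvaccinated for COVID-19. The third is a change in medical status, at the investigator's judgement.

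**The concern.** A window counted back from screening stands in for a window before the dose only when screening falls on the dose day or just before it. This protocol allows much wider gaps in both directions. The primary endpoint is the change in titer after dose 1, dose 2 and later doses, and the secondary endpoint is the incidence of vaccine-associated adverse events against healthy volunteers. Another vaccine given close to an analysed dose makes it harder to say which vaccine a reported event followed, and it could affect the measured response. The analyses in 8.4.1 and 8.4.2 mention possible covariates such as age and sex, but not other vaccination, so nothing later in the plan would pick this up.

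The rescreening text raises a different problem. Someone who failed once can be kept out in a state in which a first-time applicant would be admitted. Some planned subgroups in 8.2 have only 5 to 10 people, so avoidable refusals are unwelcome.

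**Working it through.** **Inputs.** The 14-day window back from screening and the 28-day window after a dose are from 5.2. The screening window of -7 to 0 is from 1.2 and 4.1. Enrolment after the dose is from 4.1 and 5.1. The interval between doses is not given, so it is varied below as an assumption. The plan has no figure of its own to reproduce here.

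**Days before the dose.** Put the COVID-19 dose at day 0 and screening at day s. Exclusion 1 covers days s-14 to s. The 14 pre-dose days are -14 to -1.

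- For s from -7 to -1, open days = -1 - s.
- For s = 0, open days = 0.
- For s > 0, open days = the smaller of s and 14.

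| Screening day s | Pre-dose days covered | Open |
|---|---|---|
| -7 | 8 of 14 | 6 (days -6 to -1) |
| -5 | 10 | 4 |
| -3 | 12 | 2 |
| -1 or 0 | 14 | 0 |
| +7 | 7 | 7 |
| +13 | 1 | 13 |
| +14 or later | 0 | 14 |

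Exclusion 2 starts after the dose, so it does not close the gap. When screening is before day 0, the dose day itself is also open. For a late entrant, a vaccine already given is no longer planned. For example, at s = 20 exclusion 1 covers days 6 to 20, so another vaccine given with the dose on day 0 meets neither rule.

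**Exclusion without a link to the dose.** Once s - 14 exceeds 28, that is from s = 43, the whole of exclusion 1's window lies after the 28 post-dose days. At an assumed s = 180 it covers days 166 to 180, outside both the 14 days before and the 28 days after that dose.

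**Before a later on-study dose.** Let I be the interval in days from the previous dose. Exclusion 2 covers days 1 to 28 after the previous dose, and the 14 days before the next dose are I-14 to I-1. For I of 21 or more, days covered = 43 - I, limited to between 0 and 14.

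| Assumed interval I | Covered by exclusion 2 |
|---|---|
| 21 or 28 | 14 of 14 |
| 35 | 8 |
| 42 | 1 |
| 56 or more | 0 |

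**Rescreening against entry.**

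| State of the person | First screening (5.1, 5.3) | Rescreening (5.6) |
|---|---|---|
| Failed on age or authorisation, now 3 to 11 in an authorised age group | Admitted | Age route opens only at 12 |
| Failed on age or authorisation, now 12 or older, COVID-19 vaccinated | Admitted | Age route closed |
| Failed the 14-day rule, wait now over, COVID-19 vaccinated | Admitted | 14-day route closed |

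The medical-status route carries neither condition, but it does not describe any of these three cases.

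One example shows both problems. A person is screened 10 days after another vaccine and has a COVID-19 dose booked 3 days later. They fail exclusion 1. Five days after screening, 10 + 5 = 15 days have passed since the other vaccine, but the COVID-19 dose was given 2 days earlier, so the 14-day route is closed. A first-time applicant with the same dates passes exclusion 1 and is admitted, although the other vaccine was given 10 + 3 = 13 days before the dose.

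**The case against.** The case on the other side is substantial and narrows the point.

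- **Boosters.** A reader might infer that exclusion 1 protects no booster. The documents do not support that. Already-vaccinated people who plan a booster are enrolled before it with a new baseline draw, so their screening precedes that dose. Exclusion 2 also refers to vaccination in the plural and covers the days before a next dose at short intervals. In addition, 6.1 lets an investigator withdraw someone who newly meets an exclusion criterion. What stands is the later on-study booster given well after the previous dose. No new screening precedes it, and exclusion 2 has run out.
- **Prospective entrants.** The gap is at most 6 pre-dose days plus the dose day. Screening on the dose day is allowed and leaves nothing open.
- **Age 12.** A reader might infer that 5.6 makes age 12 a general condition, or that the plan turns away young children. It does neither. Age 12 belongs to one of three routes joined by 'or', and an eligible child aged 3 to 11 is admitted at first screening. The mismatch affects only someone who consented, failed, and later became eligible. The pre-screening call in 5.7 can prevent some of those failures.
- **Effect on the endpoint.** Many late entrants without a booster plan will have no baseline value unless a stored sample exists, so they add little to a change-from-baseline comparison. Their adverse-event reports are not limited in that way.
- **Purpose of the window.** The documents give none. That it should protect the dose response is an inference, supported by exclusion 2 being counted from the dose. Later samples also serve other assays, so a screening-based window is not shown to be pointless.

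**Conclusion.** The point holds as two separate matters of alignment.

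First, exclusion 1 does not follow the dose. It can leave 6 of 14 pre-dose days and the dose day open for prospective entrants, and all 14 for people screened 14 or more days after the dose. It does not apply to later on-study boosters, where exclusion 2 covers 1 of 14 days at an assumed 42-day interval and none at 56 or more. It can also exclude late entrants for a vaccine unrelated to the dose studied. These counts take both ends of each window as included and rest on assumed dose intervals.

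Second, the age route and the 14-day route in 5.6 conflict with 5.1 and 5.3, and following them keeps out people whom a first screening would admit.

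A reader might go further and infer a biased primary comparison or a loss of power. The documents do not support either. They do not say how many people had another vaccine near a dose or how many would seek rescreening, and they give no size for any effect of co-vaccination.

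**What to change.** Reconcile 5.1, 5.2, 5.3 and 5.6:

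1. Let rescreening use the same age, authorisation and vaccination-status conditions as first entry under 5.1 and 5.3.
2. State the other-vaccine window relative to the COVID-19 dose whose response is analysed, with whatever lengths the sponsor confirms.
3. Record dates of other vaccines for all participants at entry and at each later dose, using the existing history questionnaires. Section 7.2 mentions vaccination history explicitly only for people already on another NIAID protocol, so the question should be put to everyone.
4. For doses already received at entry and for later boosters, flag samples and adverse events where another vaccine fell in the window. Report the primary and adverse-event comparisons with and without them.

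Flagging is preferable to excluding the participant or dropping the data, because either would cost observations in subgroups as small as 5 to 10. The cost is a wording amendment, one added date question and one sensitivity analysis.
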